5. RATIONALE FOR THE STUDY

Previous studies dating decades ago and now more recent GCP studies have shown that cytisine can be effective in helping smokers to stop smoking. The recent trials have shown that cytisine was more effective than placebo as well as NRT for smoking cessation with an excellent safety profile that is consistent with the safety profile reported by ██████████ for millions of subjects who have used ██████████ (cytisine). It is not possible to effectively determine which reported adverse effects associated with cytisine treatment are an effect of the drug itself, due to nicotine withdrawal effects, or a combination of both. However, the risk/benefit for cytisine appears very acceptable. Tobacco smoking contributes to some 7 million premature deaths each year worldwide.⁷ Using cytisine as a smoking cessation aid could offer far more benefit with minor risks of treatment-related adverse events when compared to the harms of continued smoking.

Achieve Life Sciences and the U.S. Food and Drug Administration (FDA) have discussed general development plans for cytisine as a new chemical entity for aiding smoking cessation in the United States (US), which ultimately led to filing an IND in 2017. The titration schedule for the commercial product comprises a gradual reduction schedule in the number of tablets per day from 6 tablets to 1 tablet over a 25 day period. However, no studies are available evaluating the dose exposure and administration schedule. This Phase 2b trial is being conducted at sites within the US to evaluate cytisine dose and administration schedules within a 25-day treatment period. Study arms will consist of the commercial 1.5 mg dose/titration schedule that is marketed in European countries, a higher dose of 3.0 mg using the marketed titration schedule, 1.5 mg and

3.0 mg doses using a three times a day (tid) schedule and respective placebo arms. The study will evaluate efficacy based on the overall reduction in the number of cigarettes smoked during the various study treatment dosing/schedules as well as compare compliance and safety profiles compared to the respective placebo arms (i.e. the marketed titration schedule or a simplified tid schedule).

Results from this study will also be used for defining Phase 3 sample size calculations when using the planned behavioral support and timing of study evaluations for the Phase 3 primary endpoint of abstinence from Week 5 to Week 8 post-randomization.

6. STUDY OBJECTIVES

6.1. Efficacy Objectives

1. Assess whether subjects randomized to cytisine, administered using the commercial titration schedule, have a greater overall reduction in cigarette smoking during the study treatment period (Day 1- 25) as compared to subjects randomized to the same placebo titration schedule.
2. Assess whether subjects randomized to cytisine, using a simplified tid schedule, have a greater overall reduction in cigarette smoking during the study treatment period (Day 1- 25) as compared to subjects randomized to the same placebo tid schedule.

6.2. Other Efficacy Objectives

Each of the following will include comparisons for 1.5 mg or 3.0 mg doses versus placebo when given as the commercial 25-day titration schedule and for the tid treatment schedule as well as comparisons between the commercial 25-day titration versus tid treatment schedules).

1. Assess the probability of abstinence from Week 5 to Week 8 post-randomization in subjects randomized to cytisine as compared to subjects randomized to placebo.
2. To compare cytisine and placebo arms on initial quit rates during study treatment, at Week 4 (End of Treatment) and on 7-day point prevalence abstinence at Week 5, Week 6, Week 7, and Week 8.
3. Among subjects abstinent at Week 4, compare time to failure to maintain abstinence through Week 8 between arms.
4. To explore potential relationships between subject-reported outcomes (e.g. anxiety, withdrawal symptoms, depression, tobacco craving, alcohol use) with the reduction in cigarette smoking during the study Treatment Period, as well as smoking cessation outcomes at Week 4 (End of Treatment) and from Week 5 to Week 8 post-randomization.
5. To explore a potential correlation for subject's nicotine metabolite ratio (NMR) with the reduction in cigarette smoking and smoking cessation outcomes.

6.3. Safety Objectives

1. To evaluate overall safety profiles of cytisine when administered at 1.5 mg or 3.0 mg, using the 25-day commercial titration or simplified tid schedules, compared to placebo.

[figure not shown]
7. STUDY DESIGN OVERVIEW

7.1. Study Design

This will be a six-arm, multi-center, double-blind, randomized, placebo-controlled, Phase 2b study conducted in male or female adults ≥ 18 years of age, smoking 10+ cigarettes daily, and willing to set a quit date that is 5-7 days after being randomized on the study. The study will be double-blinded to dose but not to the administration schedule. Study treatment must start the day after randomization such that study treatment is initiated prior to the quit date.

Subjects must meet all inclusion and exclusion criteria. Subjects will be stratified at randomization by BMI class (18.5 to <25 kg/m²; 25 to <30 kg/m²; 30 to <35 kg/m²). A total of approximately 250 subjects will be randomized 2:1 in a blinded manner to either Arm A or Arm B, vs Arm C (2:1 randomization) or Arm D or Arm E vs Arm F (2:1 randomization) as shown in Figure 2.

Figure 2: Study Design Overview

The study will be comprised of a pre-study screen, followed by twenty-five (25) days of study treatment, and post-treatment follow up visits to Week 8 post-randomization.

Each subject will receive twenty-five (25) days treatment either using the commercial titration schedule (i.e. decreasing daily tablets over the 25 days) or a simplified (tid) schedule during the Treatment Period. Smoking assessments will occur daily during the Treatment Period via self-reported cigarette count (number cigarettes smoked in the past 24 hours). Smoking abstinence

will be further assessed during the Follow-up Period starting after the Day 27±2 (Week 4) visit and documented through Week 5 (±3 days), Week 6 (±3 days), Week 7 (±3 days) and Week 8 (±3 days) post-randomization. Safety reporting will begin at randomization and continue through the Week 8 visit. The end of the study is defined as the last Week 8 visit for the last subject. Treatment assignment unblinding for subjects will not occur until the end of the study has been reached, the database has been locked, and final study analyses have been performed, unless defined as an unblinding exception in Section 7.3.4.

7.2. Treatment Schema

In order to blind the study treatment dose, all subjects will take 2 tablets at every scheduled dosing. Subjects randomly assigned to Arm A or Arm D will take one 1.5 mg cytosine tablet and one placebo tablet at each dosing. Arm B or Arm E subjects will take two 1.5 mg cytosine tablets at each dosing. Arm C and Arm F subjects will receive two placebo tablets at each daily scheduled dosing to correspond to cytosine dosing. Scheduled dosing and total daily cytosine dosing are outlined in (Table 8 and Table 9).

Table 8: Scheduled Dosing and Total Daily Cytisine Dosing for Arm A and Arm B (Commercial Titration Schedule)

Treatment Days	Daily Scheduled Dosing	Total Daily Cytisine Dose			Approximate Interval
		Placebo	1.5 mg Dose (Arm A)	3.0 mg Dose (Arm B)	
1 ^a -3	6 times daily	-	9.0 mg	18.0 mg	2 hours
4-12 ^b	5 times daily	-	7.5 mg	15.0 mg	2.5 hours
13-16	4 times daily	-	6.0 mg	12.0 mg	3 hours
17-20	3 times daily	-	4.5 mg	9.0 mg	4-5 hours
21-24	2 times daily	-	3.0 mg	6.0 mg	6 hours
25	1 time only	-	1.5 mg	3.0 mg	-

^aInitial treatment Day 1 for the 25-day Treatment Period must begin on the day after randomization.

^bQuit Date to be on Day 5, 6 or 7.

Table 9: Scheduled Dosing and Total Daily Cytisine Dosing for Arm D and Arm E (Simplified TID Schedule)

Treatment Days	Daily Scheduled Dosing	Total Daily Cytisine Dose			Approximate Interval
		Placebo	1.5 mg Dose (Arm D)	3.0 mg Dose (Arm E)	
1 ^{a,b} -20	3 times daily	-	4.5 mg	9.0 mg	4-5 hours
21 ^c -24	2 times daily	-	3.0 mg	6.0 mg	6 hours
25	1 time only	-	1.5 mg	3.0 mg	-

^aInitial treatment day 1 for the 25-day Treatment Period must begin on the day after randomization.

^bQuit Date to be on Day 5, 6 or 7.

^cThe reduction in the frequency of administrations starting on Day 21 is intended to match the corresponding reduction in the commercial titration schedule.

7.3. Discussion of Study Design

7.3.1. Placebo Control

A placebo control in this study design is necessary to control for response bias in evaluating cessation, safety and compliance outcomes. Behavioral support alone has been shown to be effective in helping smokers to quit and all subjects, including placebo control subjects, will receive behavioral support to aid their smoking cessation attempt. The treatment manipulations of interest will be study drug and the administration schedule. This Phase 2b study evaluates the effectiveness of the 1.5 mg and the 3.0 mg dose versus placebo using the commercial titration versus a simplified tid schedule. As the commercial and tid schedules will have different tablet administrations, a corresponding placebo layout is incorporated so that placebo-bias, compliance and adverse event reporting can be accurately evaluated. The use of placebo groups is therefore considered justified.

7.3.2. Efficacy Objectives

Cytisine was developed and is being marketed using a 25-day titration treatment schedule for smoking cessation using a 1.5 mg dose. The primary efficacy objective of this Phase 2b trial is to assess the overall reduction in daily cigarette smoking during the study treatment dosing/schedules compared to the respective placebo arms (i.e. the marketed titration schedule or a simplified tid schedule). Reduction in daily cigarette smoking was chosen as the primary efficacy outcome in order to better define the effects of the different dosing and schedules during the study treatment when such factors might have different daily effects on smoking behavior. A more simplified tid schedule was selected based on the pharmacokinetic profile for cytisine. In a recent pharmacokinetic trial (ACH-CYT-01), the geometric mean elimination half-life of cytisine (in the presence of food following administration of a 3 mg dose) was 4.63 h, but with a coefficient of variation of 24.3%. Given this variability, a tid administration schedule was chosen in order to ensure that subjects with a half-life at the lower end of the expected range will have adequate plasma concentrations of cytisine throughout the day.

Other efficacy results from this study will be used for defining Phase 3 sample size calculations when using the planned behavioral support and timing of study evaluations for the Phase 3 primary endpoint of abstinence from Week 5 to Week 8 post-randomization.

7.3.3. Blinding

Although subjects and site staff will be unblinded to the treatment schedule (commercial titration vs. tid) due to packaging and dose timing requirements, this remains a double-blinded study with regard to cytisine versus placebo dosing and the design therefore protects against subjective bias in reporting both efficacy and safety. Blinding will occur by coding the individual study drug packaging by an independent vendor assigned to the trial. The Sponsor and site personnel will not have access to the treatment assignment for individual subjects (except as an emergency; refer to Section 7.3.4) until the database is locked and final study analysis at 24 weeks post-randomization has been performed.

7.3.4. Unblinding

There is no intention to unblind study treatment for individual subjects. However, during the study, emergency unblinding for adverse events might need to be performed. This option may be used only if subject well-being requires knowledge of treatment assignment. The investigator must first contact the Achieve Medical Monitor, or representative, who will coordinate access to the treatment assignment code via the independent vendor. All unblinding must be documented by the site and the Sponsor.

Examples of emergencies include:

- A life-threatening, unexpected adverse event that is thought to be related to study drug and for which unblinding would change or influence treatment decisions.
- Medication error, such as an accidental overdose, that would warrant unblinding in order to more effectively manage toxicity.

7.4. Number of Subjects

A total of 250 subjects will be randomized, with approximately 50 subjects in each of the 4 treatment arms and 25 subjects in each of the two placebo arms. The maximum number of subjects that a single site is allowed to enroll, without consent of the Sponsor, is 50 (approximately 20% of the study total).

7.5. Randomization and Stratification

Sites will utilize an Interactive Response Technology (IRT) system for treatment arm assignment at randomization (Day 0). The IRT will stratify at randomization by BMI class (18.5 to <25 kg/m²; 25 to <30 kg/m²; 30 to <35 kg/m²). Detailed instructions are provided in the Study Reference Manual.

7.6. Number of Clinical Sites

This will be a multicenter clinical trial. Approximately 7-9 clinical sites in the US will participate.

7.7. Estimated Duration/Completion of Study

Duration of this study is estimated to be approximately 2 months (8 weeks) for each subject (from randomization to the Week 8 follow-up visit). Completion of the study is estimated at 6 months with ~1 months accrual ramp-up, an additional 3 months to complete accrual and 2 months from the last randomized subject to complete study follow-up evaluations.

8. SELECTION OF STUDY POPULATION

Each potential subject will be provided with an informed consent form that has been reviewed and approved by the site's governing institutional review board (IRB). In accordance with the International Conference on Harmonization (ICH) guidelines on informed consent, the Principal Investigator (or designee) will provide potential subjects with a verbal description of the study including, but not limited to, study purpose, study procedures, and risks. Potential subjects will

be asked to read the consent form and to sign and date it once all of their questions have been answered and they voluntarily agree to participate in the study. A copy of the signed informed consent form will be provided to the subject.

Upon obtaining signed informed consent, each subject will undergo the screening procedures outlined in Section 12.2.1. A screening log will be maintained by the site and will include documentation for screening failures. Subjects meeting all inclusion/exclusion criteria will then be randomized to treatment and begin the study procedures. All subjects are considered enrolled once randomized.

This clinical trial can fulfill its objectives only if appropriate subjects are enrolled. The following eligibility criteria are designed to select subjects for whom protocol treatment and procedures are considered appropriate. These eligibility criteria are the same criteria planned for the subsequent Phase 3 trials. All relevant medical and non-medical conditions should be taken into consideration when deciding whether this protocol is suitable for a particular subject.

8.1. Inclusion Criteria

Subjects must meet ALL of the following criteria to be eligible for inclusion into the study:

1. Male or female subjects, age ≥ 18 years.
2. Current daily cigarette smokers (averaging at least 10 cigarettes per day upon completing a 7-day screening diary) and who intend to quit smoking.
3. Expired air carbon monoxide (CO) ≥ 10 ppm.
4. Failed at least one previous attempt to stop smoking with or without therapeutic support.
5. Willing to initiate study treatment on the day after randomization and set a quit date that is 5-7 days after starting treatment.
6. Willing to actively participate in the study's smoking cessation behavioral support provided throughout the study.
7. Able to fully understand all study requirements, willing to participate, comply with dosing schedule, and sign the Informed Consent Form.

8.2. Exclusion Criteria

Subjects meeting ANY of the following exclusion criteria will NOT be eligible for inclusion into the study.

1. Known hypersensitivity to cytisine or any of the excipients.
2. Positive urinary drugs of abuse screen, determined within 28 days before the first dose of cytisine.
3. Clinically significant abnormal serum chemistry or hematology values within 28 days of randomization (i.e. requiring treatment).
4. Clinically significant abnormalities in 12-lead ECG determined after minimum of 5 minutes in supine position within 28 days of randomization (i.e. requiring treatment or further assessment).

5. BMI classification for being underweight ($<18.5 \text{ kg/m}^2$) or having \geq Class 2 obesity ($\geq 35 \text{ kg/m}^2$).
6. Recent history (within 3 months) of acute myocardial infarction, unstable angina, stroke, cerebrovascular incident or hospitalization for congestive heart failure.
7. Current uncontrolled hypertension (blood pressure $\geq 160/100 \text{ mmHg}$).
8. Documented diagnosis of schizophrenia or bipolar psychiatric illness; currently psychotic; having suicidal ideation (SBQ-R score ≥ 7); or current symptoms of moderate to severe depression (HAD score ≥ 11).
9. Renal impairment defined as a creatinine clearance (CrCl) $<60 \text{ mL/min}$ (estimated with the Cockcroft-Gault equation) or hepatic impairment defined as alanine aminotransferase (ALT) or aspartate aminotransferase (AST) $>2.0 \times$ the upper limit of normal (ULN).
10. Women who are pregnant or breast-feeding.
11. Male or Female subjects of child bearing potential who do not agree to use acceptable methods of birth control during the study treatment period.
12. Participation in a clinical study with an investigational drug within 4 weeks of randomization.
13. Treatment with other smoking cessation medications (bupropion, varenicline, nortriptyline, or any nicotine replacement therapy [NRT]) within 4 weeks of randomization or planned use of these other smoking cessation medications during the study.
14. Use within 2 weeks of randomization or planned use during the study of non-cigarette nicotine products (e-cigarettes, pipe tobacco, cigars, snuff, chewing tobacco, hookah) or marijuana vaping or smoking.
15. Any other reason that the investigator views the subject should not participate or would be unable to fulfill the requirements for the study.

8.3. Discontinuation of Study Drug or Study Withdrawal Prior to Week 8 Assessment

8.3.1. Discontinuation of Study Drug

Subjects can be discontinued from study drug for the reasons below. However, subjects who discontinue study drug will continue all remaining study evaluations as outlined in the protocol to obtain safety and efficacy outcomes, as if they were still taking study drug.

1. If a subject experiences a serious or intolerable adverse event that prevents them from continuing study drug.
2. At the Investigator's request (e.g. if the Investigator considers that the subject's health might be compromised by continuing study drug).

The reason for discontinuation of study drug will be recorded in the CRF.

8.3.2. Withdrawal from Study

All subjects will be informed of their right to withdraw from the study at any time and for any reason. Subjects who withdraw from the study (i.e. withdraw from further study evaluations) will be asked to complete the Day 27/EOT assessments, if still receiving study drug, and willingness to attend the Week 8 assessment visit. The date and reason for study withdrawal will be recorded on the study completion form of the CRF.

If a subject is discontinued and there is an adverse event or any abnormalities considered to be clinically significant by the investigating physician, the subject will be followed until values are considered to be clinically acceptable or deemed chronic.

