2. Review diary to verify dosing up to time of visit. Review number of cigarettes smoked in past 24 hours from subject's diary for each daily input (e.g. Days 12, 13, 14, and 15).
3. Assess for AEs and any changes to concomitant medications at the clinic visit.
4. Vital signs, including weight.
5. Review medication packs #5, #6 and #7 for compliance and collect packs #5 and #6 (which should be empty, as they contained medication for Days 11-13 and 14-15). Distribute pack #8 (for days 18-21).
6. Provide subject with behavioral support information that includes counseling ([Appendix 7](#)). NOTE: it should be stressed to subjects that even if they are smoking less, they must maintain their dosing schedule throughout the Treatment Period.
7. Blood for hematology and serum chemistry testing.
8. Remind subject of their Day 20 appointment date and time and that they must bring with them all study medication packs.

Treatment Day 20 (±1 day)

1. Subject to complete the short form of the Tobacco Craving questionnaire ([Appendix 4](#)).
2. Review diary to verify dosing up to time of visit. Review number of cigarettes smoked in past 24 hours from subject's diary for each daily input (e.g. Days 16, 17, 18, and 19).
3. Assess for AEs and any changes to concomitant medications at the clinic visit.
4. Vital signs, including weight.
5. Review medication packs #7 and #8 for compliance and collect pack #7 (which should be empty, as it contained medication for Days 16-17). Distribute final pack #9 (for Days 22-25).
6. Provide subject with behavioral support information that includes counseling ([Appendix 7](#)). NOTE: it should be stressed to subjects that even if they are smoking less, they must maintain their dosing schedule throughout the Treatment Period.
7. Blood for hematology and serum chemistry testing.
8. Remind subject of their End of Treatment (Day 27 ±2 days) appointment date and time and that they must bring with them all study medication packs.

Day 27 End of Treatment Visit (± 2 day)

1. Subject to complete the SBQ-R questionnaire ([Appendix 1](#)), the short form of the Tobacco Craving questionnaire ([Appendix 4](#)) and the HADS questionnaire ([Appendix 5](#)).
2. Collect the completed diary from subject. Review diary to verify dosing up to time of visit. Review number of cigarettes smoked in past 24 hours from subject's diary for each daily input (e.g. Days 20, 21, 22, 23, 24, and 25).

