7. SUBJECT DISPOSITION

The number of subjects who were screened, failed screening, randomized and treated will be summarized overall. The reason for failing screening will also be summarized.

The number of subjects screened, randomized, treated, discontinuing and completing study drug, completing and withdrawing from the study, as well as the number of subjects in each analysis set will be summarized for each treatment arm. In addition, the number of subjects screened, randomized and treated will be summarized by investigational site for each treatment arm.

For subjects who discontinued study drug, the reasons for discontinuation (e.g. adverse event, withdrawal by subject, physician decision) will be summarized for each treatment arm. The list of subjects who discontinued study drug will be reported, along with the reason for discontinuation.

For subjects who did not complete the study, the reasons for withdrawal (e.g. adverse event, withdrawal by subject, physician decision) will be summarized for each treatment arm. The list of subjects who withdrew from the study will be reported, along with the reason for withdrawal. Reasons will also be reported for why subjects were excluded from each analysis set. The list of subjects who are excluded from the Safety Analysis Set (subjects randomized but who never

took any study drug before discontinuing from the study) will be reported only if those subjects had safety information collected.

Attendance at each study visit will be reported with the number and percentage of subjects who attended each visit (i.e. Screening #1, Screening #2, Randomization, Treatment Day 1, etc.). Similarly, the last study visit attended will be reported with the number and percentage of subjects having their last study visit at Week 8, Week 7, etc.

The number and percentage of subjects who completed the Treatment Period (i.e., attended the Day 27 EOT) and Follow-up Assessment Period (i.e., attended the Week 8 visit) will be reported.

A Kaplan-Meier figure will be produced by treatment arm of time to last recorded data related to the abstinence endpoints (i.e., time from date of randomization to date of last smoking cessation data recorded at or prior to the Week 8 visit). Smoking cessation data includes the self-reports of cigarette smoking [number of cigarettes smoked in previous 24 hours, whether any cigarettes were smoked since the last clinic visit (yes, no) or over the past 7 days (yes, no)] and expired CO levels.

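### Protocol 8.3.2 requests exit assessments only from withdrawing subjects still on study drug, so those who stopped drug first are not asked for the end-of-treatment battery

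*Protocol*

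**What the plan says.** Protocol 8.3 separates stopping drug from leaving the study.

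- **Stopping drug (8.3.1).** The first listed reason is "If a subject experiences a serious or intolerable adverse event that prevents them from continuing study drug". After that, "subjects who discontinue study drug will continue all remaining study evaluations as outlined in the protocol". The stated purpose is to obtain safety and efficacy outcomes just as for subjects still on drug.
- **Leaving the study (8.3.2).** Subjects who withdraw from further evaluations "will be asked to complete the Day 27/EOT assessments, if still receiving study drug, and willingness to attend the Week 8 assessment visit". The second paragraph adds that if a discontinued subject has an adverse event or a clinically significant abnormality, "the subject will be followed until values are considered to be clinically acceptable or deemed chronic". That duty does not depend on being on drug.
- **Completion (SAP 7).** The SAP reports how many subjects "completed the Treatment Period (i.e., attended the Day 27 EOT" visit), and defines completing the Follow-up Assessment Period as attending Week 8. The same section tabulates, by arm, subjects "discontinuing and completing study drug, completing and withdrawing from the study", with reasons, visit attendance and last visit attended.

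**The concern.** Section 8.3.1 aims to keep data collection the same whether or not a subject still takes tablets. Section 8.3.2 then makes the last structured assessment depend on exactly that. The subjects left out include those who stopped because of an intolerable event, for whom a closing ECG, laboratory panel and SBQ-R are of particular interest.

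The completion definitions raise a second, smaller issue. They rest on visit attendance alone, while 8.3.2 invites withdrawn subjects to attend later visits. Testing the logistics and procedures planned for Phase 3 is a stated aim of the trial (Protocol synopsis, Rationale), so exit procedures and completion counts are among its outputs.

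**Working it through.** The plan states no figure on this point, so the check sets the rules against the visit schedule.

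**Step 1: who is asked.** Take three subjects on Day 10.

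| Subject | Rule | Asked for the EOT set at exit? |
|---|---|---|
| Withdraws while taking tablets | 8.3.2 | Yes |
| Stopped drug on Day 7, withdraws on Day 10 | 8.3.2 | No; asked only about Week 8 |
| Stopped drug on Day 7, stays in the study | 8.3.1 | Not applicable; all remaining visits continue, including Day 27 |

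Only the second falls in the gap. By the same wording, a subject who takes the last dose on Day 25 and withdraws on Day 26, before the EOT visit, is also off drug and not asked.

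**Step 2: what the schedule provides otherwise.** Inputs from Protocol Table 10, 12.2.3, 12.2.4, 14 and Appendix 1, and SAP 11.6:

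- ECG: screening, Day 12, Day 27; none at Week 8.
- Safety laboratory tests: screening, Days 2, 3, 6, 12, 16, 20 and 27, and Week 8.
- SBQ-R after baseline: Day 27 and Week 8.

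**Step 3: what remains for a subject already off drug at withdrawal.** Day 1 is the day after randomization, so Week 8 is Day 56 ± 3. Gap = 56 − day of last scheduled laboratory visit, using nominal visit days.

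| Withdraws on | Last labs | Gap to Week 8 labs, if they return | Post-baseline ECG | SBQ-R before Week 8 |
|---|---|---|---|---|
| Day 7 or 10 | Day 6 | 56 − 6 = 50 days (47 to 53) | None | None |
| Day 13 | Day 12 | 56 − 12 = 44 days (41 to 47) | Day 12 | None |
| Day 21 | Day 20 | 56 − 20 = 36 days (33 to 39) | Day 12 | None |

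Most of the laboratory gap comes from the withdrawal itself. An on-drug subject who does the exit set on Day 10 still has 56 − 10 = 46 days to Week 8, against 50 for the off-drug subject. What the condition removes is one set of assessments. Among these the ECG cannot be recovered at Week 8 at all, and the SBQ-R only if the subject returns.

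**Step 4: effect on the analyses.** SAP 11.6 counts ECG shifts from normal to clinically significant abnormal at any time after baseline. A subject with no post-baseline ECG cannot show one. The primary endpoint uses diary days (SAP 4.1.1). Initial quit success needs a zero-cigarette diary entry on Day 25, and anything else is a failure (SAP 4.1.2). Neither depends on the exit set in an early leaver.

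**Step 5: completion definitions.** A subject who withdraws and accepts the Week 8 invitation meets the Follow-up definition as written. For the Treatment Period, neither document says that an early exit visit is recorded as the Day 27 visit. The visit has a window of ± 2 days, and SAP 6.1 limits by-visit tables to scheduled visits. The SAP has no early-termination or visit-mapping rule.

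**The case against.** The two protocol sections do not strictly contradict each other: 8.3.1 covers subjects who remain in the study, and 8.3.2 covers those who leave it. The on-drug phrase may have been meant to separate withdrawals during treatment from withdrawals in follow-up, when the EOT visit is already done. That is plausible, but the sentence does not say so, and a site following it would not make the request.

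The second paragraph of 8.3.2 requires follow-up of known events and abnormalities. Protocol 14 allows any safety procedure at any time, and the Day 10 example already has laboratory results from Days 2, 3 and 6. All of this stands, and it rules out reading the gap as an absence of safety contact. It does not close the gap: follow-up starts from a known finding, whereas the ECG, laboratory panel and SBQ-R exist to detect unknown ones.

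Two stronger readings are tempting, and the documents support neither.

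- **Early exit visits inflate Treatment Period completion.** This needs those visits to be coded as Day 27, which no text says and the window argues against. Visit coding may be settled in the eCRF documents listed in SAP 1, which are not available here. Withdrawals are also tabulated separately.
- **The loss falls mainly on the 3.0 mg arms.** In ACH-CYT-02 (Protocol Table 5), moderate events occurred in 5/12 subjects at 3.0 mg and 2/12 at 1.5 mg (two-sided Fisher p about 0.37). That row counts severity, not stopping. The row for events leading to withdrawal of drug is zero in both groups.

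**Conclusion.** The point holds in a limited form. On its literal wording, 8.3.2 omits the standard EOT battery for subjects who stopped drug and then withdraw before Day 27. The cost per subject is one ECG, one SBQ-R and one set of laboratory tests, HADS, craving score, CO and cotinine. For those leaving before Day 12 it means no scheduled post-baseline ECG.

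This assumes that sites apply the sentence as written and that stopping drug precedes withdrawal. A subject who does both on the same day could be read either way. The number affected cannot be derived, because the documents give no rate for this sequence. The nearest evidence is 0 of 24 drug withdrawals for adverse events in ACH-CYT-02, which suggests few.

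The Follow-up completion definition literally admits withdrawn subjects who return at Week 8. The Treatment Period definition is only unclear. Priority is minor: the primary endpoint is unaffected and withdrawals are reported elsewhere.

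**What to change.** 1. **Protocol 8.3.2.** Reconcile with 8.3.1 by dropping the on-drug condition. Every subject who withdraws before the EOT visit, on or off drug, is then asked to complete the EOT assessments at withdrawal. Repair the unfinished clause about Week 8 in the same sentence.
2. **Visit labelling.** Record this as an early-termination visit with its actual study day.
3. **SAP summaries.** Include early-termination values in any-time post-baseline summaries, such as the ECG shifts in SAP 11.6, and keep them out of the Day 27 by-visit columns.
4. **SAP 7.** Count Follow-up completion only for subjects who have not withdrawn. State that Treatment Period completion means an EOT visit within Day 27 ± 2.

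The cost is one protocol sentence, short additions to the SAP and a few extra assessments using existing procedures. Reported completion may be slightly lower. The change concerns data collection only and leaves dosing and the criteria for stopping drug as they are.
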